### **3.9 Safety Analysis**

All safety analyses will be done for the Safety population.

All laboratory data will be presented in the conventional United States (US) units, as reported by the central laboratory, including normal ranges, and if an abnormal result triggers an AE reporting or not.

Final evaluation is defined to be the last evaluation performed after the first dose of study drug was taken.

#### **3.9.1 Treatment Exposure**

Treatment exposure will be calculated using the following formula:

Exposure = Last Date of Dosing – First Date of Dosing + 1.

The number of days of treatment exposure will be summarized using descriptive statistics.

#### **3.9.2 Adverse Events**

An adverse event is any untoward medical occurrence in a patient or clinical trial subject administered a medicinal product and which does not necessarily have a causal relationship with this treatment. Incidence of adverse events will be summarized for each treatment group by system organ class and preferred term. The number and percentage of subjects with each system organ class and preferred term will be presented for all subjects. Tables to summarize the incidence rates will be created for each of the following groups:

- Adverse events
- Serious adverse events
- Adverse events leading to premature discontinuation
- Adverse events by intensity
- Adverse events by relationship to study drug
- Adverse events presented in descending order of frequency by preferred term (no system organ class shown)

If a subject reports the same adverse event more than once, then that subject is only counted once for the summary of that adverse event, using the most severe intensity. The only exception to this will be for the summary by relationship to study drug. For that summary, if a subject reports the same adverse event more than once, then that subject is only counted once for the summary of that adverse event, using the most severe relationship to study drug. The same principle will be applied at the body system level summary.

If relationship to study drug are unknown then the adverse event will be summarized in the highest category of relationship to study drug. However every effort should be made to assess the relationship to the study drug before the data review. If intensity is unknown for any AEs the summary table will present the unknown category. If the start date of the adverse event is a partial date (or completely unknown) then the adverse event will be included in the summary tables (i.e. assumed to be treatment-emergent) unless the partial start date is clearly before the first dose of study drug.

Adverse events that led to premature discontinuation from the study will be listed. Serious adverse events will also be listed. These listings will contain details about the adverse event such as intensity, seriousness (only for AE leading to discontinuation) and relationship to study drug. Other supportive data, such as the subject's age, BMI, last menstrual period (for pregnancy reports) will be given.

All adverse events will be coded with MedDRA 21.0 and subsequent versions.

### **3.9.3 Hematology and Chemistry**

Hematology and chemistry mean changes from screening to the end of study visit will be summarized. The summary will present data for the screening visit and the mean change from screening to the end of study visit. The sample size, mean, SD, median, minimum, and maximum values for each treatment will be presented for each parameter.

A summary of shifts from screening to the end of study visit will be given for each parameter. The normal range for each parameter will be used to create categories of low, normal, or high. Any result that is higher (lower) than the upper (lower) limit of normal will be categorized as high (low) and any result within the lower and upper limits of normal will be categorized as normal.

Hematology and chemistry data will be located in separate tables.

### **3.9.4 Vital Signs**

Vital signs and weight mean changes from screening to the end of study visit will be summarized. Vital sign measurements will include systolic blood pressure, diastolic blood pressure and sitting heart rate. The summary will present data for the screening visit and the mean change from screening to the end of study visit. For each visit, the sample size, mean, SD, median, minimum, and maximum values will be presented for each parameter.

### **3.9.5 Vaginal Bleeding and Spotting**

Vaginal bleeding and spotting will be recorded daily by subjects in the diary. The total number of bleeding or spotting days for each subject at each treatment period will be summarized. Menstrual bleeding, intermenstrual bleeding and spotting will be summarized separately. No imputation of missing data will be performed. The number of days with diary data recorded in each treatment period will be summarized.

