### 2.3 Design

This is an exploratory, prospective, multi-center, randomized, cross-over study to assess the effect of norgestrel 75 mcg on cervical mucus and ovarian activity during reported perfect daily use and after a delayed intake of 6 hours and after a missed pill.

Women of reproductive age (18-35 years old inclusive) who meet eligibility requirements will be recruited for this study. This study has a screening period of up to 1 month to demonstrate ovulatory status prior to enrollment followed by three 28-day treatment periods (approximately 3 months) and a possible follow-up of 12 days if ovarian activity shows a follicle  $\geq 15$  mm is observed at the end of period 3 and an end of study (EOS) visit within 5 days. During the treatment period 2 the subjects will be randomized into two arms: Arm A will have a delayed pill intake of 6 hours on D42 ( $\pm 3$  days) and Arm B will have a missed pill (24-hour delayed pill intake on D42 ( $\pm 3$  days)). In the next treatment period, these subjects will cross-over meaning Arm A will have a missed pill (24-hour delayed pill intake) on D70 ( $\pm 3$  days) and Arm B will have a delayed pill intake of 6 hours on D70 ( $\pm 3$  days) (see Figure 1 below).

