### 3.7.2.5 Transvaginal Ultrasound and Hormones

Transvaginal ultrasound (TVUS) examinations will be summarized at all assessed visits for the Safety population. The following endpoints will be summarized for the screening visit, each of the 3 treatment periods, delayed pill period and missed pill period:

- Was postovulatory image seen?
- Right Ovary
  - Presence of follicles
- Left Ovary
  - Presence of follicles
- Any abnormalities found?

For each of the 3 treatment periods subjects will be counted as having the outcome (e.g, had a postovulatory image seen) if the outcome happens at least once during the treatment period. Summaries will also be done by infringement type.

TVUS largest follicle diameter measurement: The time course of the diameter will be presented graphically along with P4 and E2 (see below) at each visit.

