14.2.20	Summary of Conception Protection	ITT
14.2.21	Summary of PK Concentrations of LNG	Per-Protocol
14.2.22	Plot of PK LNG Concentrations over Time for All Periods	Per-Protocol
14.3.1.1	Incidence of Adverse Events	Safety

Table or Graph Number	Table or Graph Title	Population
14.3.1.2	Incidence of Serious Adverse Events	Safety
14.3.1.3	Incidence of Adverse Events Leading to Discontinuation	Safety
14.3.1.4	Incidence of Adverse Events by Intensity	Safety
14.3.1.5	Incidence of Adverse Events by Relationship to Study Drug	Safety
14.3.1.6	Incidence of Adverse Events Presented in Descending Frequency of Preferred Term	Safety
14.3.2.1	Listing of Subjects with Serious Adverse Events	Safety
14.3.2.2	Listing of Subjects with Adverse Events that Led to Premature Discontinuation	Safety
14.3.5.1	Summary of Treatment Exposure	Safety
14.3.5.2	Summary of Mean Change from Screening to End of Study Visit for Hematology Parameters	Safety
14.3.5.3	Summary of Mean Change from Screening to End of Study Visit for Chemistry Parameters	Safety
14.3.5.4	Summary of Shifts from Screening to End of Study Visit for Hematology Parameters	Safety
14.3.5.5	Summary of Shifts from Screening to End of Study Visit for Chemistry Parameters	Safety
14.3.5.6	Summary of Change from Screening to End of Study Visit for Vital Signs	Safety
14.3.5.7	Number of Days for Subjects with Bleeding and Spotting by Treatment Period	Safety
Listing Number	Listing Title	Population
16.2.1.1	Analysis Populations	All Enrolled
16.2.1.2	Subject Disposition	All Enrolled
16.2.1.3	Inclusion and Exclusion Criteria	All Enrolled
16.2.2	Protocol Deviations	All Enrolled

Listing Number	Listing Title	Population
16.2.3	Patients Excluded from the Analysis Populations	All Enrolled
16.2.4.1	Demographics	All Enrolled
16.2.4.2	Contraceptive History	All Enrolled
16.2.4.3	Gynecological History	All Enrolled
16.2.4.4	Pregnancy History	All Enrolled
16.2.4.5	Substance Use History	All Enrolled
16.2.4.6	Gynecological Assessments	All Enrolled
16.2.4.7	Medical History	All Enrolled
16.2.4.8	Pre-Treatment Signs and Symptoms	All Enrolled
16.2.4.9	Prior and Concomitant Medications	All Enrolled
16.2.5.1	Study Drug Administration	All Enrolled
16.2.5.2	IMP Intake	All Enrolled
16.2.5.3	PK Concentrations of LNG	All Enrolled
16.2.6.1	Cervical Mucus	All Enrolled
16.2.6.2	Transvaginal Ultrasound	All Enrolled
16.2.6.3	Hormones	All Enrolled
16.2.6.4	Ovarian Status	All Enrolled

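### Bleeding is summarised as raw day counts per period, which fall when diaries are incomplete, and the only table pools delayed-intake and missed-pill women in periods 2 and 3

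*SAP*

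**What the plan says.** Section 2.4.2 of the SAP lists two safety endpoints: adverse events and bleeding by cycle. Section 3.9.5 sets the bleeding measure: "The total number of bleeding or spotting days for each subject at each treatment period will be summarized". Menstrual bleeding, intermenstrual bleeding and spotting are shown separately. On missing diary data the section says "No imputation of missing data will be performed", and then "The number of days with diary data recorded in each treatment period will be summarized". It gives no rate, no percentage of recorded days, no minimum diary completeness and no rule for partly observed periods.

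Section 3.9 adds that "All safety analyses will be done for the Safety population". Section 3.4 defines that population by a single dose, so early stoppers are included. Under section 2.3, screening is "followed by three 28-day treatment periods".

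The one bleeding table in section 5.5 is 14.3.5.7, titled "Number of Days for Subjects with Bleeding and Spotting by Treatment Period". For transvaginal ultrasound, by contrast, section 3.7.2.5 says "Summaries will also be done by infringement type".

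**The concern.** A count of days is comparable between women only if each was observed for the same number of days. Here a woman with a full 28-day diary and a woman who recorded one week enter the same summary with the same kind of number. The planned table cannot distinguish a low total due to little bleeding from one due to few entries. The error runs one way, towards less bleeding. It is larger if women with troublesome bleeding are the ones who stop or leave the diary incomplete.

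The second issue is layout. In the crossover, delayed intake falls in period 2 for Arm A and period 3 for Arm B, and the missed pill the other way round. A table by calendar period therefore mixes the two in both periods, so the reader cannot see whether bleeding differs between them.

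**Working it through.** The SAP states no bleeding or diary-missingness figure, so there is nothing of its own to reproduce. What can be checked is how the planned measure behaves.

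**Inputs from the SAP.** 28 days per period (section 2.3); raw totals, no imputation, recorded days summarised separately (3.9.5); Safety population (3.9, 3.4); arm-to-period mapping (3.7.2.1); table by period (5.5).

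**Assumptions, not in the SAP.** Daily bleeding or spotting probability p = 0.2; days missing at random; share f of women with incomplete diaries, each with r recorded days; 1:1 allocation for the layout step.

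**Step 1: one woman.** Expected total = p × r. The full-period value is p × 28 = 5.6 days. Shortfall = 1 − r/28, which does not depend on p.

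| Recorded days r | Expected total | Shortfall | Percentage of recorded days |
|---|---|---|---|
| 28 | 5.6 | 0% | 20% |
| 21 | 4.2 | 25% | 20% |
| 14 | 2.8 | 50% | 20% |
| 7 | 1.4 | 75% | 20% |

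The last column is p × r / r. It stays at 20% because days are assumed missing at random.

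**Step 2: group mean.** Mean total = p × [(1 − f) × 28 + f × r], so the shortfall is f × (1 − r/28).

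- f = 10%, r = 21: 0.10 × 0.25 = 2.5% (5.6 becomes 5.46).
- f = 20%, r = 14: 0.20 × 0.50 = 10% (5.6 becomes 5.04).
- f = 36%, r = 7: 0.36 × 0.75 = 27% (5.6 becomes 4.09).

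In general, with a fraction m of all days missing at random, the expected recorded total is (1 − m) × the true total. For m = 5% to 20% and 5.6 days, the loss is 0.28 to 1.12 days.

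**Step 3: layout.** Suppose delayed intake adds 1 day and a missed pill adds 3. With half of each period's women in each condition, period 2 shows (1 + 3)/2 = +2 and period 3 shows (3 + 1)/2 = +2. The 2-day difference between the conditions cannot be seen. Period 1, which contains neither, still stands apart from both.

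**Step 4: limit of rescaling.** Take a woman with 6 bleeding days in 7 recorded days who then stops. Scaled to 28 days she scores 6/7 × 28 = 24. If those 6 days were one episode with no further bleeding, the full-period value would be 6. Multiplying a short record up to 28 days can therefore overstate bleeding as badly as the raw total can understate it.

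**The case against.** The other side has several sound points.

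- **The layout answers the stated endpoint.** Bleeding is defined by cycle, and the safety objective in section 2.2 concerns 12 weeks of daily use. Infringement type is tied to mucus, ovarian activity, conception protection and pharmacokinetics, not to bleeding. This stands: the plan does not contradict itself here.
- **Perfect use is not hidden.** A reader might infer that the table conceals every bleeding difference between perfect use, delayed intake and missed pill. It does not: period 1 is the perfect-use period and is shown on its own. Only the delayed-versus-missed separation is lost.
- **The incompleteness is partly disclosed.** Recorded days are summarised by period, Listing 16.2.9.6 gives the bleeding diary, and the discontinuation listing gives days on drug and reason. Bleeding reported as an adverse event leading to withdrawal also appears in those displays. This stands, but none of it adjusts the summary totals.
- **The SAP nowhere calls an unrecorded day bleed-free.** True; that is how an unscaled sum behaves, not a stated rule.
- **A rate is no cure.** Percentages of recorded days remove the bias only if missingness is unrelated to bleeding, and short records are unstable. This stands, and it rules out replacing the raw total with a value extrapolated to 28 days.
- **The consequence is limited.** The study is exploratory, with at least 45 completers planned, and section 3.9.5 attaches no test or decision to bleeding.

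**Conclusion.** The point holds in a limited form. The raw totals in section 3.9.5 are too low for women with incomplete diaries or early discontinuation, and the separate summary of recorded days reveals this without correcting it. The direction follows from the measure itself. The size cannot be obtained from the SAP: the range of 2.5% to 27% rests on assumed shares of women and recorded days missing at random, and it would be larger if heavier bleeders stop sooner.

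Table 14.3.5.7 cannot separate delayed intake from missed pill. That is lost information in a layout that otherwise matches the endpoint.

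The change is worth making because bleeding is one of only two listed safety endpoints and the denominator is already being derived. The SAP also applies comparable safeguards elsewhere: section 3.1 bases percentages on non-missing observations, section 3.7.2.1 requires at least 7 mucus assessments per period, and section 3.7.2.5 splits ultrasound by infringement type.

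**What to change.** In section 3.9.5 and Table 14.3.5.7:

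1. Keep the raw totals. Beside them report the percentage of recorded diary days with bleeding, with spotting and with intermenstrual bleeding, together with the number of recorded days.
2. Show both measures again, restricted to periods with a pre-specified minimum number of recorded days, fixed before the data are reviewed.
3. Show women who stopped during a period separately, without extrapolating their short records to 28 days.
4. Add columns for the delayed pill period and the missed pill period alongside calendar periods 1 to 3.

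The cost is a few sentences in the SAP and one re-specified table, from diary data already collected. The downside is that percentages from short records are unstable and remove the bias only if missingness is unrelated to bleeding. That is why the raw totals and recorded-day counts stay in view.

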### **3.9.6 Listing of Pregnancies**

A listing of any pregnancies that occur will be created and will include the last menstrual period date as well as details the estimated date of conception and the methods used to estimate the date of conception. The listing will also indicate which treatment period the estimated date of conception occurred.

## **5.0 APPENDICES**

### 5.1 Schedule of Assessments

Study periods	Screening visit	Treatment phase										Follow up(a)	End of study visit
		Treatment period 1	Treatment period 2				Treatment period 3						
Days	-	D1 to D28	D29 to D56				D57 to D84				D85 to D96	Between D85 and D100	
		D1 to D28	D29 to D40 ±3 And D44±3 to D56	D41±3 to D43±3		D57 to D68 ±3 And D72±3 to D84	D69±3 to D71±3						
Visits	V0	V1 1 to V1 2	V2 1 to V2 4				V3 1 to V3 4				V4 1 to V4 2	V4 3	
		Visits twice a week if follicle < 15 mm Visits every other day for a maximum of 6 days if a growing follicle ≥ 15 mm identified upon TVUS(b)	Visits twice a week if follicle < 15 mm Visits every other day for a maximum of 6 days if a growing follicle ≥ 15 mm identified upon TVUS(b)	Delayed/missed pill period Three consecutive days		Visits twice a week if follicle < 15 mm Visits every other day for a maximum of 6 days if a growing follicle ≥ 15 mm identified upon TVUS(b)	Delayed/missed pill period Three consecutive days			Visits every other day for a maximum of 12 days if a growing follicle ≥ 15 mm identified upon TVUS(c)			
				V2 1A	V2 1B	V2 1C		V3 1A	V3 1B	V3 1C			
Informed consent	X												
Inclusion/exclusion criteria	X	X											
Randomisation			X(d)										
Demographics	X												
Medical, surgical and gynecological history	X												
Physical & gynecological examination	X												
Vital signs(e)	X										X		
Laboratory tests	X										X		
Pap smear(f)	X												
STI screening	X												
High-sensitivity urine pregnancy test (β-HCG)		X(g)									X		
Dispensation of study medication (h)		X	X										

Study periods	Screening visit	Treatment phase										Follow up(a)	End of study visit	
		Treatment period 1	Treatment period 2				Treatment period 3							
Days	-	D1 to D28	D29 to D56				D57 to D84				D85 to D96	Between D85 and D100		
		D1 to D28	D29 to D40 ±3 And D44±3 to D56	D41±3 to D43±3		D57 to D68 ±3 And D72±3 to D84		D69±3 to D71±3						
Visits	V0	V1, to V1 y	V2, to V2 y				V3, to V3 y				V4, to V4 y	V4 y		
		Visits twice a week if follicle < 15 mm  Visits every other day for a maximum of 6 days if a growing follicle ≥ 15 mm identified upon TVUS(b)	Visits twice a week if follicle < 15 mm  Visits every other day for a maximum of 6 days if a growing follicle ≥ 15 mm identified upon TVUS(b)	Delayed/missed pill period Three consecutive days		Visits twice a week if follicle < 15 mm  Visits every other day for a maximum of 6 days if a growing follicle ≥ 15 mm identified upon TVUS(b)		Delayed/missed pill period Three consecutive days			Visits every other day for a maximum of 12 days if a growing follicle ≥ 15 mm identified upon TVUS(c)			
				V2 0+1	V2 0A	V2 0B	V2 0+1		V3 0+1	V3 0A	V3 0B	V3 0+1		
Study medication intake		X	X	X(i)	X(j)		X(k)	X	X(i)		X(j)	X(k)		
Diary completion		X	X	X	X	X	X	X	X	X	X	X	X	X
TVUS	X	X	X	X	X	X	X	X	X	X	X	X	X	X(l)
Mucus analysis		X(m)	X	X(n)	X(o)	X(p)	X(q)	X	X(n)	X(p)	X(o)	X(q)	X	
PK samples		X(r)(s)	X(t)	X(u)	X(v)	X(w)	X(x)	X(t)	X(u)	X(w)	X(v)	X(x)	X	
P4	X	X	X	X	X	X	X	X	X	X	X	X	X	X
E2, FSH, LH		X	X	X			X	X	X			X	X	X(y)
Prior and concomitant treatments	X	X	X	X	X	X	X	X	X	X	X	X	X	X
Adverse events and bleeding patterns	X	X	X	X	X	X	X	X	X	X	X	X	X	X

- (a) Only if follicle ≥ 15 mm is observed after Day 73 AND the criteria for stopping the extra-visits were not fulfilled by Day 84
- (b) Extra visits will be stopped before 6 days if there is no postovulatory image after 6 days
- (c) Extra visits will be stopped before 12 days if there is no postovulatory image after 6 days or if the P4 levels are > 30 nmol/L at 1 visit or > 10 nmol/L at 2 consecutive visits.
- (d) Randomization at 1st visit of treatment period 2
- (e) Vital signs include heart rate, systolic and diastolic blood pressure after at least 2-minute rest and height and weight (at screening only).
- (f) Pap smear to be performed according to current US guideline if an abnormal cervical lesion is detected during the gynecological examination
- (g) At V11 only, before first pill intake
- (h) At V11, last visit of treatment period 1 and last visit of treatment period 2
- (i) Study pill intake will be at 9 am ± 1 hour and will be noted as T2/3R-1 (actual treatment time at Day 41 or Day 69)
- (j) Study pill intake at T2/3R-1+ 6h ± 15 min
- (k) Study pill intake at T2/3R-1 ± 30 min
- (l) TVUS up to observation of postovulatory image
- (m) At V11, the mucus analysis will be performed before the 1st study medication intake
- (n) Mucus analysis to be performed at T2/3R-1 +8 h ± 30 min.
- (o) Mucus analysis to be performed at T2/3TR-1 +3h ± 15 min.
- (p) Mucus analysis to be performed at T2/3R-1 +6 h ± 15 min.
- (q) Mucus analysis to be performed within 30 min before study medication intake
- (r) Blood sampling for PK analysis at D1: subjects with even study number at predose, 2 h ± 15 min, 6 h ± 15 min and 12 h ± 30 min post-treatment and subjects with odd study number at 1 h ± 15 min, 4 h ± 15 min , 8 h ± 30 min and 24 h ± 30 min post-treatment

- (s) Blood sampling for steady state during first visit in week 3: subjects with odd numbers at predose, and between 0.5 h and 2h (morning visit), and subject with even numbers between 5 h and 9 h post-treatment (afternoon visit)
- (t) Blood sampling for compliance during 1st visit of weeks 5 and 9 within 30 min of cervical mucus sampling
- (u) Blood sampling for PK analysis at  $T2/3_{R-1} + 8h \pm 30 \text{ min}$
- (v) Blood sampling for PK analysis at  $T2/3_{R-1} + 3h \pm 15 \text{ min}$ ,  $T2/3_{R-1} + 5.5h \pm 15\text{min}$ ,  $T2/3_{R-1} + 7.5h \pm 30\text{min}$
- (w) Blood sampling for PK analysis at  $T2/3_{R-1} + 6h \pm 15\text{min}$
- (x) Blood sampling for PK analysis at  $T2/3_{R-1}$  within 30 min before study medication intake
- (y) No E2, FSH and LH measurements during extra-visits after postovulatory image is observed

## 5.2 Adjudication Committee

An adjudication committee will be convened for this study. Experts in the cervical mucus assessment and ovarian activity who are not affiliated with either of the study sites will comprise the committee. The committee will gather at study end before the database lock to review the data.

Its responsibilities will be to review data regarding IMP intake in relation to TVU results, hormonal levels and mucus scores. They will define the set of evaluable treatment cycles. They will make decisions for each subject and reach agreement on cervical mucus score and ovarian activity score/ovarian status.

A separate charter will be created to provide the details on this committee.

